5.7 Study Assessments

5.7.1 Definitions of Study Assessments

All patients will be closely monitored for safety and tolerability throughout the study. Continued dosing with HMPL-689 will be offered to patients until disease progression, death, intolerable toxicity, or at investigator's discretion that the patient can no longer benefit from the study treatment, patient withdrawal from the study, or the end of study, whichever comes first.

The schedule of activities is provided in [Appendix 1](#) and the schedule of PK sample collection at dose escalation stage is provided in [Appendix 2](#), the schedule of PK sample collection at dose expansion stage is provided in [Appendix 3](#).

5.7.2 Informed Consent Forms and Screening Log

Written informed consent for participation in the study must be obtained from the study participant before performing any study specific screening tests or evaluations using an ICF approved by the local IRB/IEC that contains all elements required by ICH E6 and in compliance with country specific regulations and guidelines. One of the original signed ICFs for enrolled patients and for patients who are not subsequently enrolled will be maintained at the study site within the subject source documentation.

All screening evaluations must be completed and reviewed to confirm that patients meet all eligibility criteria before study treatment. Patients who do not meet the lab testing related eligibility criteria might be re-screened. Re-screening requires re-signing of the ICF and a new screening number will be assigned. Upon implementation of Amendment 5, patients may not be rescreened. The investigator will maintain a screening log to record details of all patients' screened and record reasons for screening failure. Eligibility verification form will be maintained by investigator and confirmed with sponsor prior to initial study treatment.

5.7.3 Medical History and Demographic Data

Medical history and demographic data will be collected at screening. The participant's consent gives the principal investigator, sponsor, sponsor's designees, and regulatory authorities, if applicable, direct access to obtain information from the patient's medical records, including electronic medical records, for the purpose of reviewing information about the participant's health

which is necessary as part of the implementation of the research project as well as for statutory control purposes, including self-regulation, quality control, and monitoring.

Medical history will include clinically significant diseases, surgeries, cancer history (including constitutional symptom/B-symptoms [Unexplained weight loss $\geq 10\%$ over previous 6 months, fever $>38^{\circ}\text{C}/100.5^{\circ}\text{F}$ for 2 or more weeks without other evidence of infection, night sweats for more than 1 month without evidence of infection]), prior cancer diagnosis (including tumor type, initial diagnosis date, immunohistochemistry, flow cytometry, other pathological findings), prior anti-neoplastic therapies and procedures and related outcome, use of tobacco, use of alcohol and drugs of abuse prior to the screening visit.

Demographic data will include date of birth, sex, and self-reported race/ethnicity.

5.7.4 Concomitant Medication/Concomitant Procedure

Any concomitant medication/procedure within 7 days prior to the screening visit and 30 days after the end of treatment or early termination will be recorded.

5.7.5 Performance Status

The ECOG performance status ([Appendix 9](#)) should be assessed by the same study personnel at screening, Days 1 and 15 of Cycle 1, and Day 1 of every cycle from Cycle 2 onwards, and at study completion or early termination, if possible. Care will be taken to accurately score performance status, especially during screening for study eligibility purposes. Additional consideration should be given to borderline ECOG performance status to avoid enrolling patients with significant impairment.

5.7.6 Ann Arbor Staging and Rai/Binet Staging

[Appendix 10](#) provides a description of Ann Arbor staging for primary nodal lymphomas.

[Appendix 11](#) and [Appendix 12](#) provide a description of Rai and Binet staging respectively for CLL.

Ann Arbor staging and Rai and/or Binet staging will be collected at screening.

5.7.7 International Prognostic Index

[Appendix 13](#) provides information on the different International Prognostic Indices (IPIs) for the patients with FL, MCL, LPL/WM and other lymphomas. For FL, risk factors refer to Follicular Lymphoma International Prognostic Index (FLIPI). For MCL, risk factors refer to Simplified Mental Cell Lymphoma International Prognostic Index (SMIPI). For LPL/WM, risk factors refer to International prognostic scoring system for Waldenström's macroglobulinemia (ISSWM). For DLBCL and other lymphomas, risk factors refer to IPI.

IPI score will be collected at screening.

5.7.8 Vital Signs

Vital signs will be collected at screening, Days 1, 8, 15, 22 of Cycle 1, Days 1 and 15 of Cycle 2, Day 1 of every cycle from Cycle 3 and onwards, and at study completion or early termination, and will include measurements of body temperature, heart rate, respiratory rate, systolic and diastolic blood pressure while the patient is in a seated position. The patient should be seated for 5 minutes before the measurement of the blood pressure.

5.7.9 Physical Examination

Physical examination refers to the examination of all body systems, including assessment of head, eyes, ears, nose, larynx, neck, heart, chest, abdomen, limbs, skin, lymph nodes, nervous system, general condition, weight, and height. Physical examination should be performed at screening, Days 1, 8, 15, 22 of Cycle 1, Days 1 and 15 of Cycle 2, Day 1 of every cycle from Cycle 3 and onwards, and at study completion or early termination. Weight will be assessed at screening, Day 1 of every cycle from Cycle 2 and onwards, and at study completion or early termination, while height will be assessed only at screening. After screening, a change of physical signs from baseline, and newly presented or patient-reported physical signs should be evaluated. As part of tumor assessment, limited physical examinations should also include the evaluation of the presence and degree of enlarged lymph nodes, skin lesions, hepatomegaly, and splenomegaly.

5.7.10 Laboratory Assessments

Samples for hematology, chemistry panel, serum amylase and lipase, fasting lipid profile, coagulation, thyroid hormones, hemoglobin A1c, serum β -2 microglobulin, viral serology, urinalysis, leukocyte immunophenotyping and pregnancy testing will be analyzed at the study site's local laboratory. Upon implementation of Protocol Amendment 5, some assessments will no longer be required. Please refer to [Appendix 1](#) for further details.

Laboratory assessments will include the following:

- Hematology consists of complete blood count, including red blood cell count, hemoglobin, hematocrit, reticulocyte count, WBC count with differential (neutrophils, bands, lymphocytes, eosinophils, monocytes, basophils, and other cells), and platelet count. Hematology should be tested at screening (within 7 days prior to the first dose of the IP), Days 8, 15 and 22 of Cycle 1, Days 1 and 15 of Cycle 2, Day 1 of every cycle from Cycle 3 and onwards, and at study completion or early termination.
- The chemistry panel includes blood urea nitrogen (BUN) or urea, sodium, potassium, magnesium, chloride, calcium, phosphorus, uric acid, fasting glucose, ALT, total and direct bilirubin, AST, alkaline phosphatase (ALP), LDH, protein (total), albumin, creatine phosphokinase, creatinine, and estimated CrCl per Cockcroft-Gault. Chemistry should be tested at screening (within 7 days prior to the first dose of the IP), Days 3, 8, 15 and 22 of Cycle 1, Days 1 and 15 of Cycle 2, Day 1 of every cycle from Cycle 3 and onwards, and at study completion or early termination.
- Serum amylase and lipase should be tested at screening (within 7 days prior to the first dose of the IP), Days 8, 15 and 22 of Cycle 1, Days 1 and 15 of Cycle 2, Day 1 of every cycle from Cycle 3 and onwards, and at study completion or early termination.
- Fasting lipid profile: includes total cholesterol, high-density lipoprotein (HDL), low-density lipoprotein (LDL), triglycerides, and should be tested at screening (preferably

within 7 days prior to the first dose of the IP), Day 1 of every odd cycle from Cycle 3 and onwards, and at study completion or early termination.

- Coagulation (INR, aPTT, or PT) should be tested at screening (within 7 days prior to the first dose of the IP), Day 1 of every cycle from Cycle 2 and onwards, and at study completion or early termination.
- Thyroid hormones include free triiodothyronine (FT3), free thyroxine (FT4) and thyroid stimulating hormone (TSH), and should be tested at screening (preferably within 7 days prior to the first dose of the IP), Day 1 of every odd cycle from Cycle 3 and onwards and at study completion or early termination.
- Hemoglobin A1c should be tested at screening (preferably within 7 days prior to the first dose of the IP), Day 1 of every odd cycle from Cycle 3 and onwards and at study completion or early termination.
- Serum β -2 microglobulin (β 2M) should be tested at screening (preferably within 7 days prior to the first dose of the IP), Day 1 of every cycle from Cycle 2 and onwards, and at study completion or early termination.
- Viral serology should be tested at screening and includes the following:
 - HIV
 - HBV (HBsAb, HBsAg and HBcAb)
 - also, HBsAb by enzyme-linked immunosorbent assay and HBV DNA by PCR if the patient is HBcAb positive
 - HCV (HCV antibody)
 - also HCV RNA by PCR if the patient is HCV antibody positive
 - CMV (CMV immunoglobulin G [IgG], CMV immunoglobulin M [IgM])
 - also CMV DNA by PCR if patient is CMV IgG positive
- Urinalysis or dipstick (glucose, protein, ketones, blood), should be tested at screening (within 7 days prior to the first dose of the IP), Day 3 and 15 of Cycle 1, Days 1 and 15 of Cycle 2, Day 1 of every cycle from Cycle 3 and onwards, and at study completion or early termination. If protein $\geq 2+$ observed during the period of study treatment, a 24-hour urine test should be conducted within 1 week.
- Leukocyte immunophenotyping (Fluorescence-activated Cell Sorting [FACS] subsets) should be done at screening (preferably within 7 days prior to the first dose of the IP), Day 15 of Cycle 1, Day 1 of every cycle from Cycle 2 and onwards, and at study completion or early termination, which includes:
 - Determination of T/B/NK Counts (CD3, CD4, CD8, CD19, CD16/56) using a standard cell marker panel
- Patients with CLL: (optional)
 - Tests of cytogenetic abnormality will be performed at screening (preferably within 7 days prior to the first dose of the IP) for patients with CLL in the dose expansion stage only. These tests should include but not be limited to TP53 mutation, 17p deletion, 11q deletion, 13q deletion, and +12 trisomy.
 - Upon implementation of Protocol Amendment 5, these assessments will no longer be required.
- All women who are not postmenopausal (no menses for 12 months without an alternative medical cause) or surgically sterile will have a serum β -HCG or urine pregnancy test at

screening and at study completion or early termination. In the case of postmenopausal women, the date of menopause onset should be recorded.

- Plasma HMPL-689 concentrations (for PK evaluations) will be assessed using a validated assay. Blood samples should be collected according to the time points in [Appendix 2](#) or [Appendix 3](#).
- Exploratory biomarker assessments will be required for patients in the dose expansion stage and should be collected according to the time points in [Appendix 4](#).
 - Upon implementation of Protocol Amendment 5, this assessment will no longer be required.
- LPL/WM related testing
 - Serum immunoglobulins assessment (quantitative immunoglobulin assessment of IgM, IgA, IgG) will be performed for patients with LPL/WM at screening (preferably within 7 days prior to the first dose of the IP), Day 1 of every cycle from Cycle 2 and onwards, study completion or early termination, quarterly during the extended PFS follow-up period, and at the time of CR confirmation.

5.7.11 Electrocardiogram

All electrocardiograms (ECGs) are required to be performed using a 12-lead tracing. ECG measurements will include PR interval, QRS interval, RR interval, QT/QTcF interval, and heart rate.

For dose escalation stage, triplicate ECGs, approximately 2 minutes apart, should be performed at screening, pre-dose, and 2 ± 0.5 and 4 ± 0.5 hours post-dose on Days 1 and 15 of Cycle 1 in order to evaluate concentration-QT relationship with HMPL-689. Single ECG will be conducted at any time on Day 1 of every cycle from Cycle 2 and onwards, and at study completion or early termination. For dose expansion stage, ECGs should be collected according to the schedule and time points in [Appendix 3](#).

Additional ECGs and other cardiac monitoring will be provided as clinically indicated during the study.

5.7.12 Echocardiogram/MUGA

An echocardiogram/multigated acquisition scan (MUGA) to assess left ventricular ejection fraction (LVEF) will be conducted at screening, Day 1 of every odd cycle from Cycle 3 and onwards, and at study completion or early termination. The modality of the cardiac function assessments must be consistent within a patient. For example, if echocardiogram is used for the screening assessment, then echocardiogram should also be used for subsequent scans if required.

5.7.13 Tumor and Response Evaluation

The baseline tumor assessment can be completed within 21 days prior to the first dose of IP (depending on the patient's disease status a window may be acceptable based on a discussion between the investigator and the sponsor's medical monitor). All measurable and evaluable lesions should be assessed and documented at screening and each subsequent tumor evaluation, using blood test, physical examination, contrast enhanced CT scans (neck, chest, abdomen, and pelvis) for non-fluorodeoxyglucose (FDG)-avid lymphomas (e.g., LPL/WM, CLL/SLL, and MZL) and/or positron emission tomography(PET)-CT scans for patients with FDG-avid lymphomas

(e.g., FL, MCL, and DLBCL). Enhanced magnetic resonance imaging (MRI) may be used instead of CT scans in patients for whom CT scans are contraindicated.

Tumor assessment will be conducted every 8 weeks (± 7 days) for the first 24 weeks and every 12 weeks (± 7 days) thereafter. Patients who discontinue HMPL-689 treatment due to reasons other than disease progression will continue tumor assessment according to previous tumor assessment schedule till disease progression, death, end of the study, or start of a new anti-neoplastic therapy, whichever is earlier (see [Appendix 1](#)). Upon implementation of Protocol Amendment 5, patients who discontinue HMPL-689 treatment due to reasons other than disease progression will also discontinue from the study.

The same imaging procedure and laboratory tests used to define measurable lesions at baseline should be used throughout the study for each patient.

Bone Marrow Aspirate and Biopsy

A bone marrow biopsy or aspirate is strongly recommended to be done at baseline or up to 3 months before of the Cycle 1 Day 1 and for confirmatory purposes for all patients who achieved a radiologic CR or to confirm suspected progressive disease (PD) based solely upon declines in the platelet count and/or hemoglobin. Upon implementation of Protocol Amendment 5, this assessment will no longer be required.

5.7.14 Timing of Study Assessments

5.7.14.1 Screening and Assessment

All screening evaluations must be completed and reviewed by the investigator and the sponsor's medical monitor to confirm that patients meet all eligibility criteria before the first administration of HMPL-689.

Please see [Appendix 1](#) for the schedule of screening and pre-treatment assessments. Screening and pre-treatment tests will be performed within 21 or 7 days preceding the day of first dose of IP, unless otherwise specified. Results of standard of care tests performed prior to obtaining informed consent and within 21 days prior to study entry may be used; such tests do not need to be repeated for screening.

The baseline tumor assessment can be completed within 21 days prior to the first dose of IP (depending on the patient's disease status a window may be acceptable based on a discussion between the investigator and sponsor's medical monitor). A bone marrow biopsy and aspirate are to be done at baseline or up to 3 months before study treatment.

5.7.14.2 Assessment during Treatment

All visits must occur within ± 3 days (± 1 day during the DLT assessment window) from the scheduled date, unless otherwise noted ([Appendix 1](#)). All assessments will be performed on the day of the specified visit unless a time window is specified.

5.8 Participant Completion/Discontinuation

5.8.1 Study Completion/Early Termination Visit

Patients who complete the study or discontinue from the study early will be asked to return to the clinic at 30 ± 7 days after the last HMPL-689 administration for a follow-up visit. Ongoing AEs considered by the investigator to be related to HMPL-689 will be followed up until the event has resolved to baseline, the event is assessed by the investigator as stable, new antineoplastic treatment is initiated, the patient is lost to follow-up, the patient withdraws consent, or when it has been determined that the study treatment or participation is not the cause of the event.

5.8.2 Extended Progression Free Survival Follow-up

Patients who discontinue HMPL-689 treatment due to reasons other than disease progression will enter the extended PFS follow-up period. During this period, tumor assessment will be conducted quarterly until disease progression, death, the end of the study or the initiation of new antineoplastic therapy, whichever comes earlier. The assessments to be performed at the follow-up visits are listed in [Appendix 1](#). Upon implementation of Protocol Amendment 5, patients who discontinue HMPL-689 treatment due to reasons other than disease progression will also discontinue from the study.

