In a phase 2, multi-center, open-label trial to evaluate the safety and efficacy of umbralisib in previously treated NHL patients, a total of 208 patients were enrolled, including 69 MZL, 117 FL, and 22 SLL. MZL patients were refractory to at least one line of anti-CD20, and FL/SLL patients were refractory to at least two lines of therapy, including an anti-CD20. The ORR in FL patients was 45.3% with 5.1% CR and DoR of 11.1 months (range 8.3-15.6 months). The median TTR was 2.8 months (range 2.7 to 2.9). The ORR in MZL patients was 49.3% with 15.9% CR and DoR not yet reached at time of publication. The median TTR was 2.8 months (range 2.7 – 2.9). Safety data revealed serious adverse events in 28.1% of patients, with 24.6% \geq grade 3. The most common \geq grade 3 AEs were neutropenia (11.5%), diarrhea (10.1%) and increased ALT/AST (7.2%). Other AEs of interest included pneumonitis (all grade 1.4%; \geq grade 3 1.0%), and colitis (all grade 1.4%; \geq grade 3 0.5%) (Zinzani 2020).

Overall, approved PI3k- δ inhibitors have demonstrated a modest ORR in the range of 40% to 50% in FL and MZL. However, they demonstrate a low CR rate of 1-16% and mPFS of less than 12 months. While these agents represent a manageable toxicity profile, high rates of diarrhea, colitis, and hepatic toxicity results in a high rate dose reduction and treatment discontinuation, thereby impacting the long term benefit. Therefore, there is room for a more efficacious and tolerable PI3K- δ inhibitor for treatment of NHL (Dreyling 2017, Zinzani 2020, Flimm 2019).

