5.8.4 Study Treatment Discontinuation

Patient must discontinue the study treatment in case of:

- Disease progression
- Intolerable toxicity
- Use of new antineoplastic therapy
- Pregnancy with onset during study

The primary reason for study treatment discontinuation should be recorded on the appropriate CRF. Discontinuation from HMPL-689 treatment does not mean discontinuation from the study, and the remaining study procedures should be completed as indicated in the study protocol.

In addition, stopping rules for a cohort or study during dose escalation (Section 5.8.4.1) and dose expansion (Section 5.8.4.2) stages are outlined below.

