NCI-CTC National Cancer Institute Common Toxicity Criteria NCI CTCAE National Cancer Institute Common Terminology Criteria for Adverse Events NHL Non-Hodgkin Lymphoma nPR Nodular Partial Response ORR Objective Response Rate	MTD	Maximum Tolerated Dose
NCI CTCAE National Cancer Institute Common Terminology Criteria for Adverse Events NHL Non-Hodgkin Lymphoma nPR Nodular Partial Response ORR Objective Response Rate	MZL	Marginal Zone Lymphoma
Adverse Events NHL Non-Hodgkin Lymphoma nPR Nodular Partial Response ORR Objective Response Rate	NCI-CTC	National Cancer Institute Common Toxicity Criteria
nPR Nodular Partial Response ORR Objective Response Rate	NCI CTCAE	
ORR Objective Response Rate	NHL	Non-Hodgkin Lymphoma
•	nPR	Nodular Partial Response
PCFB Percentage Change from Baseline	ORR	Objective Response Rate
	PCFB	Percentage Change from Baseline

Protocol Number: 2018-689-00US1 Page 10 of 43

PDProgressive Disease PFS Progression Free Survival PK Pharmacokinetics PR Partial Response PR-L Partial Response with Lymphocytosis PT Preferred Term PTCL Peripheral T-cell Lymphoma QD Once Daily RP2D Recommended Phase 2 Dose SAP Statistical Analysis Plan SOC System Organ Class SDStable Disease SLLSmall Lymphocytic Lymphoma SRC Safety Review Committee TEAE Treatment-Emergent Adverse Event

TTR Time to Response

VGPR Very Good Partial Response WHO World Health Organization

WHO-DD World Health Organization Drug Dictionary

Note: Standard units such as mg and mL as used in the text are not included in the abbreviations list.

2. Introduction

This document describes the rules and conventions to be used in the presentation and analysis of efficacy and safety data for Protocol 2018-689-00US1. It describes the data to be summarized and analyzed, including specifics of the statistical analyses to be performed. The pharmacokinetics (PK) part will not be documented in this SAP and a separate analysis plan for PK analysis will be developed.

This statistical analysis plan (SAP) is based on protocol amendment 5 (dated 08Dec2022) and CRF version 6 (dated 13Jan2023).

Per protocol amendment 5, the end of the study is defined as 18 months after the last patient has been enrolled in the study or all patients have discontinued the study treatment, whichever comes earlier.

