7	No post-baseline tumor	Date of first dose	Censored	No post-baseline
	No post-baseline tumor evaluable assessment and alive			assessment
7 8	No post-baseline tumor evaluable assessment and alive New anti-cancer treatment	Date of last evaluable	Censored	assessment Initiation of new anti-
	No post-baseline tumor evaluable assessment and alive			assessment

		treatment or date of first dose (if no post- baseline tumor assessment before new anti-cancer)		
9	No disease progression or death Note: use last tumor assessment before two or more consecutive missed/non-evaluable tumor assessments (if exists)	Date of last evaluable	Censored	Progression free at time of analysis: the patient is known to be alive without any progression happened at the data cut- off date

Note: Only for tumor assessments and death date before cutoff date.

[a] time period that identifies two consecutive missed/non-evaluable tumor assessments is calculated as 2*(the planned duration between assessments + protocol allowed visit window) from the last evaluable tumor assessment or (2*the planned duration between assessments + 1*protocol allowed visit window) from date of first dose (if no post-baseline evaluable tumor assessment).

According to protocol, tumor assessment will be conducted every 8 weeks for the first 24 weeks and every 12 weeks thereafter (±7 days). Given the schedules visit assessment scheme, the definition of two missed consecutive tumor assessment visit may vary, please refer to following rule:

- If the last evaluable tumor assessment before PD/death is on or before Day 105 (week 15, which is 8 weeks before week 24, and allowing for 7 days for early visit, hence 7*16 weeks 7 days for a late visit =Day 105), then two consecutive assessments equates to 126 days since last evaluable tumor assessment, allowing for early and late visits (2*8 weeks + 7 days for an early assessment + 7 days for a late assessment), or 119 days since date of first dose, allowing for late visit (2*8 weeks + 7 days for a late assessment).
- If the two missed assessments occur over the period when the scheduled frequency of tumor assessments change from 8-weekly to 12-weekly, which means last evaluable tumor assessment is from week 16 to 23 (Day 106 to Day 161), then two consecutive assessments equates to 154 days (7*8 weeks + 7*12 weeks + 7 days for an early assessment + 7 days for a late assessment) since last evaluable tumor assessment.

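### SAP Table 2 has no censoring reason for leaving the study without progression, so after Amendment 5 such patients are reported as known progression-free at cut-off

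*Protocol*

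**What the plan says.** **Protocol.** Section 5.8.2 states that after Amendment 5 "patients who discontinue HMPL-689 treatment due to reasons other than disease progression will also discontinue from the study". Section 5.7.13 repeats the rule, and the synopsis and Section 4.1.7 drop the extended PFS tumour assessments. Section 5.8.4 still says the opposite in general terms: "Discontinuation from HMPL-689 treatment does not mean discontinuation from the study".

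**SAP.** The Introduction says "This statistical analysis plan (SAP) is based on protocol amendment 5 (dated 08Dec2022"), so the plan was written with the exit rule in force. Section 16.5, Table 2 lists nine PFS situations. None covers study exit, withdrawal of consent or loss to follow-up. Row 9 takes patients with neither progression nor death, censors them at the last evaluable assessment, and gives as the reason that "the patient is known to be alive without any progression happened at the data cut"-off date. Section 16.5 tabulates the censoring reasons as categories and lists them by patient. Section 16.6 applies the same censoring rules to DoR. No sensitivity analysis is planned for either endpoint.

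**The concern.** After exit there are no scheduled scans. General adverse event collection ends 30 days after the last dose, or at new therapy if earlier (Protocol 6.2.5). Neither survival nor progression status at cut-off is therefore known for these patients, yet the table says that it is. A reader of the censoring table cannot separate patients followed without progression from patients lost to view.

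The distinction matters because stopping may be related to prognosis. Protocol 4.1.2 allows stopping for toxicity, for an investigator's judgement that benefit has ended, or by withdrawal. Protocol 2.4 says that toxicity with the approved drugs of this class "results in a high rate dose reduction and treatment discontinuation". If risk rises after stopping, a Kaplan-Meier estimate that treats these exits as non-informative is too favourable for PFS and DoR.

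**Working it through.** **1. Which row takes the patient?** Take a patient who stops drug without progression and leaves the study.

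- Recorded death: rows 1-2.
- Recorded new therapy: row 8, or row 5 if progression follows it.
- No evaluable baseline scan, alive: row 6.
- No evaluable post-baseline scan, alive: row 7, censored at first dose.
- Everyone else: row 9 only.

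The date rule in row 9 is sound, since it credits no time after the last evaluable scan. The stated reason is what fails.

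**2. Do the missed-visit rules deal with exit?** The SAP windows reproduce: 2 × (56 + 7) = 126 days; 2 × 56 + 7 = 119; 56 + 84 + 14 = 154; 2 × (84 + 7) = 182. They decide whether a later recorded event counts. They do not identify a patient who has left and has no later record.

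**3. How large could the effect on PFS be?** The plan gives no figure to reproduce, so this is an illustration. Inputs:

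- On-drug median 11 months: idelalisib in relapsed indolent NHL, Protocol 2.4, borrowed as an assumption. λ = ln 2 / 11 = 0.0630 per month.
- Stopping without progression at δ = 0.02 or 0.04 per month (assumed; the documents give no rate). Share stopping first = δ/(λ + δ) = 0.02/0.0830 = 24%, or 0.04/0.1030 = 39%.
- Hazard after stopping = rλ, with r = 1.0, 1.5 or 2.0 (assumed).
- Exit rule in force from first dose.

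Kaplan-Meier with exit at stopping estimates e^(−λt): median 11.0 months and, at 12 months, e^(−0.756) = 46.9%, whatever r is. With full follow-up,

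S(t) = e^(−(λ+δ)t) + [δ/(λ + δ − rλ)] × [e^(−rλt) − e^(−(λ+δ)t)].

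Example, δ = 0.04, r = 2, t = 12: 0.2905 + (0.04/−0.0230) × (0.2204 − 0.2905) = 0.2905 + 0.1218 = 41.2%.

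| δ | r | True median (months) | True 12-month PFS |
|---|---|---|---|
| either | 1.0 | 11.0 | 46.9% |
| 0.02 | 1.5 | 10.5 | 45.2% |
| 0.02 | 2.0 | 10.2 | 43.9% |
| 0.04 | 1.5 | 10.2 | 43.7% |
| 0.04 | 2.0 | 9.6 | 41.2% |

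The overstatement runs from 0 to 11.0 − 9.6 = 1.4 months, and from 0 to 46.9 − 41.2 = 5.7 percentage points.

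**4. Does it depend on the median?** Yes. Protocol 2.4 also gives 3.7 months (idelalisib in mantle cell lymphoma). The same δ and r then give a true median of 3.5-3.7 against 3.7 months.

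**5. What would counting exits as events do?** If every exit is an event at the stop date, the median is ln 2/(λ + δ): 0.693/0.0830 = 8.3 months (true value 10.2-11.0) or 0.693/0.1030 = 6.7 months (true value 9.6-11.0). That lies further from the modelled truth than Kaplan-Meier does, so it is a bound and not a correction.

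**The case against.** Three stronger readings are tempting, and the documents support none of them.

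- *That PFS and DoR are shown to be biased by informative censoring.* Nothing in either document says that hazard changes after stopping. At r = 1 the bias is zero. The high discontinuation rate in Protocol 2.4 describes approved comparators; the same section calls the tolerability of HMPL-689 favourable.
- *That patients are carried as progression-free up to cut-off.* They are not. Row 9 censors at the last evaluable scan, and only its label refers to cut-off.
- *That exits are hidden.* SAP 9.1 summarises and lists the reasons for leaving treatment and study, 16.5 adds reverse Kaplan-Meier follow-up, and 16.8 plans a swimmer plot. What is missing is the link between exit and the PFS and DoR censoring reason.

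The exit rule also starts only when Amendment 5 is implemented, after enrolment had been halted. Patients who stopped earlier were due quarterly scans, so a model that applies the rule from first dose overstates the exposure. PFS and DoR are secondary, descriptive endpoints of a phase 1 study, and no test or decision rule rests on them.

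It can fairly be said that Protocol 5.8.4 is general text and that 5.7.13 and 5.8.2 are dated and specific. The contradiction still stands in the current protocol. The Table 2 point does not depend on how it is settled, because Section 4.1.7 drops the extended assessments in any case.

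All of this limits the size of the point. None of it makes the row 9 label true for a patient who has left.

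**Conclusion.** The point holds as a reporting defect with a possible, undemonstrated bias behind it. Table 2 was not adapted to the exit rule, and row 9 gives an unsupported reason for patients who left with an evaluable post-baseline scan and no recorded death or new therapy.

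Under the assumptions above, median PFS could be overstated by 0 to 1.4 months and 12-month PFS by 0 to 5.7 points. For those stop rates and hazard ratios this is an upper bound, because the rule covers only the period after Amendment 5 and the SAP pools both periods. With a short median the effect is negligible. No figure was derived for DoR; it inherits the same rules and so the same ambiguity. This should be corrected, but it does not threaten the study's primary conclusions, which concern dose and safety.

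**What to change.** 1. Split row 9 into (a) on study and progression-free at cut-off and (b) left the study without documented progression, by recorded reason. Keep the last evaluable scan as the censoring date for both. Tabulate (a) and (b) separately for PFS and DoR.
2. Optionally, add one sensitivity analysis for each endpoint counting (b) exits for toxicity or investigator decision as events at the stop date. Label it a conservative lower bound with respect to those exits, not a corrected estimate.
3. Reconcile Protocol 5.8.4 with 5.7.13 and 5.8.2.

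The cost is SAP wording, one split category in existing tables and, if wanted, one extra analysis. SAP 9.1 already draws discontinuation reasons from the End of Treatment and End of Study forms, so item 1 should need no new data. How finely those forms code the reasons cannot be seen in the documents and should be checked before item 2 is written.
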